8.5.1.4. Treatment of Outliers in Pharmacokinetic Analysis

If a value is considered to be anomalous due to being inconsistent with the expected PK profile, it may be appropriate to exclude the value from the PK analysis. However, the exclusion of any data must have strong justification and will be documented in the CSR.

Any quantifiable predose concentration value will be considered anomalous and set to missing for the PK analysis.

8.5.2. Presentation of Pharmacokinetic Data

Individual concentrations deemed to be anomalous will be flagged in the listings and excluded from the summary statistics.

For PK concentration data the following rules will apply:

- Values that are BLQ will be set to 0 for the calculation of summary statistics.
- Arithmetic mean or median values that are BLQ will be presented as 0.
- If any BLQ results (treated as 0) are in a series of summarized data, geometric mean and coefficient of variation (CV) of geometric mean will be reported as not calculated (NC).

For PK parameters the following rule will apply:

- For the calculation of summary statistics of PK parameters, all not reported (NR) and not calculated (NC) values in a data series will be set to missing.
- The AUC values will be set to NC if they have been calculated using fewer than 3 concentrations, and/or 3 concentrations if the last is C_{max} .
- Geometric mean and CV will not be calculated for t_{max} .

8.5.3. Pharmacokinetic Statistical Methodology

All PK concentrations and parameters will be listed.

Summary tables, mean (+ standard deviation [SD]) figures, overlaying individual figures, and individual figures by analyte and time postdose will be provided for plasma PK concentrations. All PK concentration figures will be produced on both linear and semi-logarithmic scales, with the exception of figures across all days, which will be produced on the linear scale only. The +SD bars will only be displayed on the linear scale.

Summary tables by treatment will be provided for all PK parameters, with the exception of diagnostic regression-related PK parameters. Summary statistics (n, Mean, SD, CV, minimum, median, maximum, geometric mean [Geom Mean] and geometric CV [Geom CV]) will be calculated for plasma LOXO-305, caffeine, paraxanthine, omeprazole and S-warfarin

PK parameters. Excluded subjects will be listed in the PK parameter tables, but will be excluded from the statistical analysis and summary statistics and noted as such in the tables.

A statistical analysis will be conducted to investigate the drug-drug interaction on the PK of the following comparisons:

- LOXO-305 plus caffeine (test) versus caffeine alone (reference) To test the drug-drug interaction on the PK of caffeine and paraxanthine
- LOXO-305 plus omeprazole (test) versus omeprazole alone (reference)
- LOXO-305 plus warfarin (test) versus warfarin alone (reference)

The natural log-transformed³ PK parameters (AUC_{0-t} , $\text{AUC}_{0-\text{inf}}$, C_{\max} , and MRAUC for paraxanthine only) will be analyzed using a mixed model.⁴ The model will include actual treatment as a fixed effect, and subject as a random effect.

For each PK parameter separately, the least squares mean (LSM) for each treatment, difference in LSMs between the test and reference treatments, and corresponding 90% confidence interval (CI) will be calculated; these values will then be exponentiated to give the geometric least squares mean, geometric mean ratios, and corresponding 90% CI.

Additionally, the pooled estimate (across all treatments) of the within-subject CV will be calculated, and residual plots will be produced to assess the adequacy of the model(s) fitted.

Examples of the SAS code that will be used are as follows:

Mixed Model Analysis

```
proc mixed data = <data in>;
  by parcatln parcat1 paramn param;
  class trtan usubjid;
  model lpk = trtan / cl residual ddfm = kr2;
  lsmeans trtan / cl pdiff = reference('1') alpha = 0.1;
  random intercept / subject = usubjid(trtseqp);
  ods output lsmeans = <data out>;
  ods output diffs = <data out>;
  ods output covparms = <data out>;
run;
```

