6. STUDY TREATMENTS

The study treatment sequence name and ordering to be used in the TFLs are presented in [Table 1](#).

Table 1: Presentation of Study Treatment Sequence in TFLs

Study Treatment Sequence Label
Probe Drug Cocktail (D1-5)/ 200 mg LOXO-305 QD (D6-14)/ 200 mg LOXO-305 QD + Probe Drug Cocktail (D15-19)/ 200 mg LOXO-305 QD (D20)

QD = once daily; TFL = table, figure, and listing.

Error! Reference source not found. shows a list of the PK treatment labels and ordering that will be used in the TFLs.

Table 2: Pharmacokinetic Treatment Labels

Study Treatment Labels	Order in TFLs
200 mg caffeine	1
200 mg LOXO-305 QD + 200 mg caffeine	2
40 mg omeprazole	3
200 mg LOXO-305 QD + 40 mg omeprazole	4
10 mg warfarin	5
200 mg LOXO-305 QD + 10 mg warfarin	6
200 mg LOXO-305 QD	7

QD = once daily; TFL = table, figure, and listing.

The study treatment names and ordering to be used in the TFLs are presented in [Table 3](#).

Table 3: Presentation of Study Treatment Labels in TFLs (Safety)

Study Treatment Labels	Order in TFLs
Probe Drug Cocktail*	1
200 mg LOXO-305 QD	2
200 mg LOXO-305 QD + Probe Drug Cocktail*	3

QD = once daily; TFL = table, figure, and listing.

*200 mg caffeine + 40 mg omeprazole + 10 mg warfarin + 10 mg Vitamin K

All treatments described above are the planned treatments. The TFLs will reflect the actual treatments received.

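### Does the fixed reference level '1' in the SAP's example SAS code leave the omeprazole and S-warfarin contrasts without a reference?

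*SAP*

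**What the plan says.** SAP 8.5.3 first sets out the analysis in words. It lists three comparisons, each probe given with LOXO-305 (test) against that probe alone (reference). The caffeine comparison also serves paraxanthine. Log-transformed AUC0-t, AUC0-inf and Cmax, plus MRAUC for paraxanthine, go into a mixed model with actual treatment fixed and subject random. The difference in least squares means between test and reference, with its 90% CI, is exponentiated. The geometric least squares mean for each treatment is reported as well.

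A code block follows, introduced by "Examples of the SAS code that will be used are as follows". Four of its lines matter here:

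- "by parcatln parcat1 paramn param" (separate models, presumably by analyte and PK parameter)
- "class trtan usubjid"
- "lsmeans trtan / cl pdiff = reference('1') alpha = 0.1"
- "random intercept / subject = usubjid(trtseqp", closed by a bracket

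SAP section 6 holds two treatment numberings. Table 2, for PK, is introduced with the words "shows a list of the PK treatment labels and ordering that will be used in the TFLs". It runs from caffeine (1) through "200 mg LOXO-305 QD + 40 mg omeprazole" (4) to LOXO-305 alone (7). Table 3, for safety, is introduced with "The study treatment names and ordering to be used in the TFLs are presented in" and numbers the probe cocktail alone 1, LOXO-305 alone 2 and the combination 3. Neither table mentions `trtan`, and no other part of the SAP defines it.

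**The concern.** Read with Table 2, the code appears to make caffeine alone the reference in every model. The omeprazole models would hold only levels 3 and 4, and the S-warfarin models only 5 and 6, so the named reference would not exist in them. Those two probes carry the whole CYP2C19 and CYP2C9 assessment, and this mixed model is the only inferential analysis in the study.

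A second worry is direction. Protocol 8.3.2 names the probe alone first and the combination second, while the SAP puts the combination first as test. A hurried repair of the reference line could invert a ratio, so that a geometric mean ratio of 2.0 would print as 1/2.0 = 0.50.

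The block has one more loose end. It nests subject within `trtseqp`, which is not in the CLASS statement.

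**Working it through.** No power, sample size or event count is at issue: Protocol 8.1 sets up to 16 subjects without statistical considerations. The one figure to match is the confidence level, and it agrees: 1 − 0.90 = 0.10, the alpha in the code.

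**Step 1. Count the models (SAP 8.5.3).** Caffeine 3, paraxanthine 4 (MRAUC counted once), omeprazole 3, S-warfarin 3. Total 3 + 4 + 3 + 3 = 13.

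**Step 2. Look for level 1 under each numbering in SAP section 6.**

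| Analyte | Models | Levels if `trtan` follows Table 2 | Levels if it follows Table 3 |
|---|---|---|---|
| Caffeine | 3 | 1, 2 | 1, 3 |
| Paraxanthine | 4 | 1, 2 | 1, 3 |
| Omeprazole | 3 | 3, 4 | 1, 3 |
| S-warfarin | 3 | 5, 6 | 1, 3 |
| **Models lacking level 1** | | **3 + 3 = 6 of 13** | **0 of 13** |

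Coding 1 and 2 within each analyte also gives 0 of 13. The result depends entirely on a variable that the SAP leaves undefined.

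**Step 3. What the reference choice can change.** Each model compares two treatments, so there is one pairwise difference d on the log scale, with standard error s and t quantile q. Test over reference is exp(d), with limits exp(d − qs) and exp(d + qs). Swapping the reference gives exp(−d) = 1/exp(d), with limits exp(−d − qs) and exp(−d + qs), which are the reciprocals of the same limits in reverse order. The information is identical.

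A simulated paired example shows this, assuming n = 16, a true ratio of 0.80 and a within-subject CV of 30% (neither the ratio nor the CV is from the documents):

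- test/reference: 0.809 (90% CI 0.681 to 0.961)
- reference/test: 1.236 (1.041 to 1.469)
- check before rounding: 1/0.8088 = 1.236, 1/0.9607 = 1.041, 1/0.6809 = 1.469

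The estimates depend on the assumed values; the reciprocity does not.

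**Step 4. Possible outcomes if level 1 were absent.** With two treatments there are three: no contrast is printed, the intended contrast is printed, or its reciprocal is printed. The first leaves an empty cell for a planned primary comparison. The third gives a ratio that contradicts the two geometric means reported with it. Protocol 8.5 requires independent peer review of all tables and a review of drafts at a dry run, so either should be caught.

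**Step 5. The random statement.** SAP Table 1 has a single sequence label and the design is fixed-sequence. Nesting subject within a quantity that takes one value picks out the same subjects, so the intended model is still the one in the prose: subject as a random effect.

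**The case for a change.** The strongest argument for a change is that Table 2 is the PK table and Table 3 is labelled for safety, so a reader of the PK section would naturally take `trtan` from Table 2. The sentence introducing the code also says that it will be used. For CYP2C19 the expected direction is not obvious: Protocol 1.3 reports induction in vitro with no detectable inhibition, while Protocol 3.2 lists weak inhibition. A plausibility check on the omeprazole ratio might therefore miss an inversion. The correction would take a few lines.

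Part of this stands. If `trtan` does follow Table 2, the printed line needs '3' for omeprazole and '5' for warfarin, and `trtseqp` serves no purpose. The rest does not carry through to a result. The block is called an example and contains dataset placeholders, so the prose is the specification, and the prose fixes the reference for each probe. Direction is fixed there too, as test against reference. The Protocol's word order sets no numerator, and SAP section 1 says that the SAP supersedes the Protocol on statistical matters. Detecting an inversion does not depend on pharmacological expectation, because the ratio can be compared with the two geometric means. The 2.0-to-0.50 scenario also needs a mistaken repair that neither document proposes.

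**Conclusion.** No change to the plan is needed. At its widest, the slip touches 6 of 13 models, and only if `trtan` carries Table 2's display numbers; with the probe alone coded 1 in each model it touches none. In neither case does it alter the contrast, the model, the 90% level or the sample size. An analyst following the text of SAP 8.5.3 obtains the intended ratio for each probe.

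This rests on two assumptions: that the BY variables separate the analytes, so that each model holds one probe-alone and one combination treatment, and that the prose governs where example code is loose. Defining `trtan` in the programming specification would tidy the code but change no estimate, interval or conclusion.

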8.6. Safety and Tolerability Assessments

8.6.1. Adverse Events

All AEs will be coded using the Medical Dictionary for Regulatory Activities (MedDRA) Version 23.0. All AEs will be assigned severity grade using National Cancer Common Terminology Criteria for Adverse Events (CTCAE) Version 5.0.

A treatment-emergent adverse event (TEAE) will be defined as an AE that starts during or after the first dose, or starts prior to the first dose and increases in severity after the first dose.

A treatment-related TEAE will be defined as a TEAE with a relationship of related to the study treatment LOXO-305 and probe drugs and vitamin K, as determined by the investigator.

The assignment of TEAEs to the treatments will be as follows:

- A TEAE occurring during or after Day 1 dosing and prior to Day 6 dosing will be assigned to Probe Drug Cocktail/or 10 mg vitamin K
- A TEAE occurring during or after Day 6 dosing and prior to Day 15 dosing will be assigned to 200 mg LOXO-305
- A TEAE occurring during or after Day 15 dosing will be assigned to 200 mg LOXO-305 + Probe Drug Cocktail/or 10 mg vitamin K

All AEs will be listed. In addition to the data recorded in the database, the listings will include derived onset time and duration. Onset time will be calculated from the time of the last dose for TEAEs only.

The frequency of subjects with TEAEs and the number of TEAEs will be summarized for the following categories:

- TEAEs (overall, serious, leading to discontinuation, and leading to death) by treatment
- TEAEs by severity and treatment
- Treatment-related TEAEs (overall, serious, leading to discontinuation, and leading to death) by treatment
- Treatment-related TEAEs by severity and treatment

The frequency of subjects will be summarized separately for TEAEs and treatment-related TEAEs by the following:

- System organ class, preferred term, and treatment
- Preferred term and treatment

For the AE data the following rules will apply:

- For the derivation of TEAE status: If the start date/time of an AE is incomplete or missing, an AE will be assumed to be a TEAE, unless the incomplete start date/time or the end date/time indicates an AE started prior to the first dose.
- For the derivation of treatment-related TEAE status: If the study treatment relationship for a TEAE is missing, a TEAE will be assumed to be a treatment-related TEAE.

- For the derivation of onset time: If the start date/time of an AE is missing, onset time will not be calculated. If the start date/time of an AE is incomplete, where possible, the minimum possible onset time will be calculated and presented in ' \geq DD:HH:MM' format (eg, if the date/time of the last dose is 01MAY2019/08:00 and recorded start date/time of an AE is 03MAY2019, then the minimum possible onset time will be calculated by assuming the AE started at the first hour and minute of 03MAY2019 [03MAY2019/00:00], thus will be presented as onset time \geq 01:16:00 in the listing).
- For the derivation of duration: If the end date/time of an AE is missing, duration will not be calculated. If the start or end date/time of an AE is incomplete, where possible, the maximum possible duration will be calculated and presented in ' \leq DD:HH:MM' format (eg, if the start of an AE date/time is 01MAY2019/08:00 and its recorded end date/time is 03MAY2019, then the maximum possible duration will be calculated by assuming the AE ended at the last hour and minute of 03MAY2019 [03MAY2019/23:59], thus will be presented as duration \leq 02:15:59 in the listing).
- For the calculation of summary statistics: If a subject experienced multiple TEAEs with the same preferred term for the same treatment, this will be counted as 1 TEAE for that treatment under the maximum severity recorded.

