4. STUDY DESIGN

This is a Phase 1, open-label, 2-period, fixed-sequence drug-drug interaction study to investigate the effect of multiple oral doses of LOXO-305 on the PK of single oral doses of caffeine (CYP1A2 substrate) and its metabolite paraxanthine, S-warfarin (CYP2C9 substrate), and omeprazole (CYP2C19 substrate) in healthy subjects.

In Period 1, Day 1, 200 mg caffeine (tablet), 40 mg omeprazole (capsule), and 10 mg warfarin (tablet) administered as a single dose of probe drug cocktail, along with 10 mg vitamin K (tablets), will be administered in the morning following a fast of at least 10 hours predose and 2 hours postdose. Blood samples for concentrations of the substrates (caffeine/paraxanthine, omeprazole, and S-warfarin) in plasma will be collected predose through 120 hours postdose on Day 1. Of these samples, samples will be analyzed for concentrations of caffeine/paraxanthine from predose through 24 hours postdose, for concentrations of omeprazole [REDACTED], and for concentrations of [REDACTED].

There will be a washout period of 5 days between administration of the probe drug cocktail on Day 1 and the first dose of LOXO-305 on Day 6.

[figure not shown]
In Period 2, on Days 6 through 19, oral doses of 200 mg LOXO-305 will be administered once daily (QD) for 14 consecutive days in the morning at the actual time of the Day 1 probe drug cocktail dosing (\pm 1 hour). On Day 15, LOXO-305 will be coadministered with 200 mg caffeine (tablet), 40 mg omeprazole (capsule), and 10 mg warfarin (tablet) administered as a single dose of probe drug cocktail, along with 10 mg of vitamin K (tablets) at the actual time of the Day 1 probe drug cocktail dosing (\pm 1 hour) following a fast of at least 10 hours predose and 2 hours postdose. On Days 7 through 11, and Days 13, 14, 16, 18, and 19, subjects will fast for at least 2 hours predose and 1-hour postdose. On Days 6, 12, and 17 where clinical laboratory evaluations are performed, subjects will fast for at least 8 hours predose and 1 hour postdose. Blood samples for concentrations of LOXO-305 in plasma will

CCI

CCI. Samples collected CCI. CCI LOXO-305 dosing CCI. Blood samples for concentrations of the substrates (caffeine/paraxanthine, omeprazole, and S-warfarin) in plasma will be CCI; of these samples, samples will be analyzed for concentrations of caffeine/paraxanthine from CCI, for concentrations of omeprazole CCI, and for concentrations of CCI.

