A schematic of the study design is presented in [Figure 1](#).

Figure 1: Study Design

EOT= end of treatment; ET = early termination; ICF = informed consent form.

The start of the study is defined as the date the first subject who is enrolled in the study signed an Informed Consent Form (ICF). Note that enrolled subjects are defined as those subjects who are assigned to receive a dose of study drug; this definition excludes screen failure subjects. Replacement subjects may be enrolled only if deemed necessary by the Sponsor.

Subjects who are determined to be screen failures are permitted to be re-screened if the Investigator (or designee), with agreement from the Sponsor, feels that the subject may meet

eligibility criteria upon re-screen. Re-screened subjects will be provided a new subject number.

To assess their eligibility to enter the study, potential subjects will be screened within 34 days (Days -35 to -2) and be admitted to the Clinical Research Unit (CRU) on Day -1 (Check-in).

Subjects will be confined at the CRU from the time of Check-in (Day -1) until End of Treatment (EOT) on Day 23 upon completion of all PK and safety assessments or Early Termination (ET) if the subject discontinues. Dosing of probe drug cocktail will occur on Day 1 and Day 15 and dosing of LOXO-305 will occur on Days 6 through 19. A follow-up phone call will occur for all subjects who received at least 1 dose of study drug (including subjects who are terminated early) 7 days (\pm 2 days) after EOT or ET. The duration of participation is expected to be approximately 67 days (Screening through follow-up phone call).

In this study, physical examinations, 12-lead ECGs, vital sign measurements, How Do You Feel? inquiries, clinical chemistry panel, coagulation parameters, hematology panel, urinalysis, and recording of concomitant medications will be performed at specified times during the study.

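### SAP 8.6.1 tabulates crude TEAE counts by treatment over windows of 5, 9 and at least 8 days, states no end for the last window, and gives no time at risk

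*SAP*

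**What the plan says.** SAP 8.6.1 sets three assignment rules:

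- Cocktail: "A TEAE occurring during or after Day 1 dosing and prior to Day 6 dosing will be assigned to Probe Drug Cocktail" (the label adds vitamin K).
- LOXO-305 alone: "A TEAE occurring during or after Day 6 dosing and prior to Day 15 dosing will be assigned to 200 mg LOXO-305".
- Combination: "A TEAE occurring during or after Day 15 dosing will be assigned to 200 mg LOXO-305 + Probe Drug Cocktail/or 10 mg vitamin K". No end is given.

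Collection is bounded elsewhere. SAP section 4 confines subjects "until End of Treatment (EOT) on Day 23" and collects AEs regardless of causality to that point. From EOT to the follow-up call, 7 ± 2 days later, only events judged drug-related are collected, plus all SAEs.

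For the overall, severity and treatment-related tables, "The frequency of subjects with TEAEs and the number of TEAEs will be summarized for the following categories", each by treatment. The tables by system organ class and preferred term give subject counts only. No table carries days at risk or a rate.

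SAP Table 3 makes the three windows the safety columns. The sequence label in SAP Table 1 divides time differently: cocktail D1-5, LOXO-305 D6-14, combination D15-19, then LOXO-305 at D20. SAP 8.6.6 plans no inference on safety.

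**The concern.** A longer window collects more events even if the treatments do not differ. With crude counts side by side, a reader who sets cocktail alone against cocktail plus LOXO-305, to judge what LOXO-305 adds, compares 5 days with 8 or more. The distortion runs against LOXO-305.

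The open third window adds a second problem. The column for all TEAEs takes in every AE to Day 23 and then only related AEs and SAEs to the follow-up call. It therefore covers no single defined period. For related TEAEs and SAEs the imbalance is larger, and it reaches the contrast named in the secondary objective.

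At stake is how a descriptive safety table in up to 16 subjects is read. No test or decision rule depends on it.

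**Working it through.** The documents state no AE rate or expected count, so there is no figure of theirs to reproduce.

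**1. Window lengths, by day subtraction**

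- Cocktail: Day 1 to Day 6 dosing, 6 − 1 = 5 days. SAP section 4 agrees: "There will be a washout period of 5 days between administration of the probe drug cocktail on Day 1" and the first LOXO-305 dose.
- LOXO-305 alone: Day 6 to Day 15 dosing, 15 − 6 = 9 days.
- Combination, all-cause: Day 15 dosing to EOT, 23 − 15 = 8 days.
- Combination, related AEs and SAEs: the call falls on Day 23 + 7 ± 2 = Day 28 to 32, so 13 to 17 days (nominal 15).

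The ± 1 hour dosing tolerance is negligible: 192/121 = 1.59 to 192/119 = 1.61, against 192/120 = 1.60.

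**2. Event counts under a constant rate and no drug effect.** The expected ratio is the ratio of window lengths.

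- Combination to cocktail, all-cause to EOT: 8/5 = 1.60. This is an upper value, because SAP 8.6.1 counts repeats of one preferred term within a treatment once.
- Combination to cocktail, related AEs and SAEs: 13/5 = 2.6 to 17/5 = 3.4.
- Combination to LOXO-305 alone, all-cause: 8/9 = 0.89.
- Combination to LOXO-305 alone, related AEs and SAEs: 13/9 = 1.44 to 17/9 = 1.89.

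**3. Subjects with at least one TEAE.** With rate L per subject-day and window T, the expected share is 1 − exp(−L·T). L is an assumption, so it is varied. One anchor can be built from the protocol. In the healthy-volunteer midazolam study (sections 1.4 and 1.4.1), 3 of 15 subjects dosed for 13 days reported AEs, so L = −ln(1 − 3/15)/13 = 0.017. This takes observation as equal to the dosing days, and it is an on-treatment rate rather than a true background rate.

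| L per day | 5 d | 9 d | 8 d | 8 d / 5 d | 8 d / 9 d | Subjects of 16: 5 d, 8 d |
|---|---|---|---|---|---|---|
| 0.01 | 4.9% | 8.6% | 7.7% | 1.58 | 0.89 | 0.8, 1.2 |
| 0.017 | 8.2% | 14.3% | 12.8% | 1.56 | 0.90 | 1.3, 2.1 |
| 0.03 | 13.9% | 23.7% | 21.3% | 1.53 | 0.90 | 2.2, 3.4 |
| 0.05 | 22.1% | 36.2% | 33.0% | 1.49 | 0.91 | 3.5, 5.3 |
| 0.10 | 39.3% | 59.3% | 55.1% | 1.40 | 0.93 | 6.3, 8.8 |
| 0.30 | 77.7% | 93.3% | 90.9% | 1.17 | 0.97 | 12.4, 14.5 |

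**4. Effect of a time denominator.** With 16 completers the all-cause subject-days are 16 × 5 = 80, 16 × 9 = 144 and 16 × 8 = 128. At L = 0.05 the expected events are 4.0, 7.2 and 6.4, which is 5.0 per 100 subject-days in every column. The ratio returns to 1.0.

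**5. Table 1 against 8.6.1.** An event on Day 21 belongs to the combination under 8.6.1. In Table 1 the combination ends at D19, and a LOXO-305 segment at D20 follows. SAP section 4 has LOXO-305 dosing on Days 6 through 19. These passages must be reconciled.

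**The case against.** The strongest reply is that the most distorted all-cause contrast is not one the trial sets out to make. The secondary objective concerns LOXO-305 alone and coadministered. Those all-cause windows are 9 and 8 days, with expected subject ratios of 0.89 to 0.93 at rates up to 0.10 per day. The safety analysis is descriptive, SAP 8.1 already urges caution because of the sample size, and at the anchor rate the cocktail and combination columns differ by less than one subject in 16. Listings will give onset time and duration for every AE. The table shells, which are not available here, may show window lengths. All of this stands and limits the weight of the point. It does not cover related AEs and SAEs, and onset in the listings runs from the last dose, so a reader would have to rebuild time at risk by hand.

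A reader might infer that events in the last days before EOT are off-drug and wrongly labelled. The documents do not support that. Protocol section 1.4.2 gives a half-life of about 20 hours in patients, so about 2^(−24/20) = 44% remains 24 hours after the last dose. Protocol section 1.6 keeps subjects in the unit for 96 hours to let the drug clear. By the same test, 4 of the 5 cocktail days would also be off-drug.

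A reader might also want the combination column cut to the first 120 hours to match the cocktail column. That would turn the objective's all-cause contrast from 9 against 8 days into 9 against 5 (expected event ratio 5/9 = 0.56).

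**Conclusion.** The point holds as a matter of presentation, and it is cheap to correct. Crude counts over 5, 9 and 8 days would inflate the combination relative to cocktail alone by about 1.4 to 1.6 times for subjects at rates up to 0.10 per day, falling to about 1.2 at 0.30, and by up to 1.6 times for all-cause events. For related AEs and SAEs, the observation-time ratio to cocktail alone is 2.6 to 3.4.

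These figures assume a constant rate, full follow-up and equal ascertainment. The last is doubtful, because procedures differ by period and the time after EOT is covered by one phone call.

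Two stronger readings fail. A fixed statement that the combination will look 1.5 times worse is not supported, since that value depends on an assumed rate. Nor is the safety objective's comparison biased throughout: it is nearly balanced for all-cause AEs and unbalanced only for related AEs and SAEs. Likewise, the missing end belongs to the assignment rule; collection itself does stop, at EOT or the follow-up call depending on AE type.

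**What to change.** In SAP 8.6.1 and the table shells:

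- State the end of each window by AE type: for the combination, EOT (or ET) for all-cause AEs, and the follow-up call for related AEs and SAEs.
- Reconcile these windows with the day ranges in SAP Table 1.
- Keep the planned subject and event counts. Add subject-days at risk to each column, computed from actual dosing and exit times, and report TEAEs per 100 subject-days.
- Show events collected after EOT separately, so that each all-cause column covers a defined period.
- Leave the combination column at its full length to EOT.

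The cost is SAP and shell wording plus an extra row or column in the AE tables. The rates will be imprecise with up to 16 subjects. For example, 4 events in 80 subject-days is 5.0 per 100, with an exact 95% Poisson interval of about 1.4 to 12.8 (limits ½χ²(0.025; 8) = 1.09 and ½χ²(0.975; 10) = 10.24 events, each divided by 80). They should be presented as descriptive only.

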8.4. Safety Analysis

All safety assessments, including AEs, SAEs, vital sign measurements, clinical laboratory results, physical examination results, concomitant medications, and 12-lead ECGs, will be tabulated and summarized where possible, using descriptive methodology, as needed, by timepoint. Unless otherwise specified, baseline value is defined as the last non-missing measurement before administration of study drug on Day 1, Period 1. No formal statistical analyses are planned for the safety data. All safety data will be listed by subject.

Concomitant medications will be coded using the World Health Organization (WHO) Drug Dictionary (WHO Drug Global B3, September 2019). Adverse events will be coded using Medical Dictionary for Regulatory Activities (MedDRA) Version 22.1 (or higher). The incidence of AEs will be presented by severity and by relationship to study drug as determined by the Investigator or designee ([Appendix 1](#) for AE reporting). All TEAEs will be summarized by system organ class and preferred term.

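### SAP 8.6.1 plans to report the number of TEAEs, but its rule for repeats would turn that into a count of subject-by-term pairs whenever a term recurs within a treatment

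*SAP*

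**What the plan says.** SAP 8.6.1 introduces its first group of AE tables with "The frequency of subjects with TEAEs and the number of TEAEs will be summarized for the following categories". The categories are TEAEs overall, serious, leading to discontinuation and leading to death; "TEAEs by severity and treatment"; and the same two sets for treatment-related TEAEs. So a subject count and an event count are both planned, including by severity.

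The second group, by system organ class and preferred term, is narrower: "The frequency of subjects will be summarized separately for TEAEs and treatment-related TEAEs by the following". Only subjects are counted there.

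Among the handling rules that close the section, one begins "For the calculation of summary statistics: If a subject experienced multiple TEAEs". Its trigger is "If a subject experienced multiple TEAEs with the same preferred term for the same treatment", and its result is "this will be counted as 1 TEAE for that treatment under the maximum severity recorded". It is not restricted to subject counts, and neither document gives a separate rule for event counts.

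The SAP also states "All AEs will be listed". Protocol 8.4 says only that "The incidence of AEs will be presented by severity and by relationship to study drug" and contains no rule for repeats.

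**The concern.** Counting a subject once per preferred term, at the worst grade, is the usual convention for subject incidence. Here the unit reduced to one is the TEAE itself, and the rule covers every AE summary statistic. Both documents define a TEAE as an individual adverse event with its own start, so a reader will take the number of TEAEs to mean the number of event records.

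What an event count adds to a subject count is recurrence. The secondary objective is the tolerability of multiple LOXO-305 doses, and LOXO-305 is given daily for 14 days. If a term did recur in a subject within one treatment, the event column would hide it and would disagree with the listing. The severity table would keep only the worst occurrence.

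**Working it through.** The documents give no planned AE count or rate, so there is no figure to reproduce. The check is a direct count followed by an illustration of scale.

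**1. The rule applied to one subject.** Suppose a subject has headache three times under one treatment, at grades 1, 1 and 2.

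| Quantity | Every event counted | SAP rule as written |
|---|---|---|
| Subjects with a TEAE | 1 | 1 |
| Number of TEAEs | 3 | 1 |
| of grade 1 | 2 | 0 |
| of grade 2 | 1 | 1 |

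The subject count is the same either way; the event count is not. If all three were grade 1, the total would still fall from 3 to 1, but no grade would vanish from the table. The two effects therefore need different conditions: a repeat within subject, term and treatment for the first, and mixed grades among those repeats for the second.

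**2. What the rule leaves open.** It fixes severity only. It does not say which relationship or seriousness a merged event keeps when the repeats differ, although counts of treatment-related and serious TEAEs are planned.

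**3. What the sponsor's healthy-volunteer studies show (protocol 1.4 and 1.4.1).**

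- LOXO-BTK-20008 gave 200 mg once daily on 13 consecutive days, the closest design to this one. It reports 7 AEs in 3 subjects: injection site pain, nasal congestion, flatulence, constipation, increased urinary frequency, facial rash and skin tear. That is seven different terms, so the rule would remove 7 − 7 = 0 events.
- LOXO-BTK-20007 Part 2 gave a single oral dose plus an intravenous microtracer. It reports 6 AEs in 4 subjects: venipuncture-site tenderness twice, antecubital bruising three times (two left, one right) and one allergic reaction. Each subject had at least one event, so distinct subject-by-term pairs number between 4 and 6. The rule would remove 6 − 6 = 0 to 6 − 4 = 2 events (0% to 33%), depending on whether repeats fell in the same subject, which is not stated.

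**4. Scale under an assumed rate.** Assume that events of one preferred term follow a Poisson distribution with mean m per subject per treatment, with 16 subjects (the maximum in protocol 8.1). The value of m is not in the documents.

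- Expected events listed: 16 × m
- Expected events counted under the rule: 16 × (1 − e^−m)
- Share lost: 1 − (1 − e^−m)/m

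| m | Listed | Counted | Share lost |
|---|---|---|---|
| 0.1 | 1.6 | 1.52 | 4.8% |
| 0.25 | 4.0 | 3.54 | 11.5% |
| 0.5 | 8.0 | 6.30 | 21.3% |
| 1.0 | 16.0 | 10.11 | 36.8% |

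The treatment windows in SAP 8.6.1 differ in length: Day 1 to Day 6 is 5 days, Day 6 to Day 15 is 9 days, and Day 15 to end of treatment on Day 23 is 8 days. At an assumed constant 0.05 events per day (m = 0.25, 0.45 and 0.40), the share lost would be 11.5%, 19.5% and 17.6%, so any loss need not be equal across treatments. These figures show how the rule behaves; they do not predict this trial.

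**The case against.** The strongest reply is that this is a disclosed convention with little practical effect. The rule is pre-specified in the section that promises the counts. Every AE is listed with derived onset time and duration, so true counts can be recovered. Subject frequencies, including all the system organ class and preferred term tables, are untouched. The protocol asks only for incidence, no inferential safety analysis is planned, and no decision depends on an event count. The authors may have meant the rule for subject counts only. The table shells that accompany the SAP, which are not among the documents reviewed, may define the event column differently.

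All of that stands and limits the weight of the point. It does not remove it: the sentence as written covers event counts, and a programmer who follows it would merge them.

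A reader might go further and infer that recurrent events on daily LOXO-305 will be understated, citing the 0% to 33% range from LOXO-BTK-20007 Part 2. The documents do not support that. The study was single-dose, five of its six events were venipuncture tenderness or phlebotomy bruising, none was considered related to LOXO-305, and it is not stated that any repeat was in one subject. The daily-dosing study reports no repeated term. A reader might also infer that lower-grade events will vanish from the severity tables. All healthy-volunteer TEAEs summarized in protocol 1.4.1 were Grade 1, so nothing there shows the mixed grades that this would need.

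**Conclusion.** The point holds in conditional form. SAP 8.6.1 plans to report event counts and then applies to them a rule that fits only subject counts. Followed literally, it produces subject-by-term pairs per treatment under the label of number of TEAEs.

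If any subject repeats a term within a treatment, the tabulated number will be below the number listed. If the repeats differ in grade, the lower grades will also drop out of the event counts by severity. If no term recurs, tables and listings agree and the effect is zero. The size cannot be estimated from the documents; the percentages above rest on an assumed Poisson model and assumed rates. LOXO-BTK-20008 suggests the loss may well be nil, though its data are preliminary and come from few AEs.

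This is a minor correction to a descriptive safety summary. It has no bearing on the primary objective.

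**What to change.** Limit the rule to subject counts and add the missing rule for events. Suggested text for SAP 8.6.1:

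*For the number of subjects, multiple TEAEs of the same preferred term within a treatment count once at maximum severity; for the number of TEAEs, every TEAE is counted at its own severity.*

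Counted this way, each event also keeps its own relationship and seriousness, which closes the gap in step 2 of the check. If the sponsor prefers the merged count, the alternative is to relabel the statistic as the number of distinct subject-by-preferred-term occurrences and to state how differing relationship and seriousness are resolved.

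The cost is one sentence in the SAP and a check that the table shells agree. Data collection, listings, subject frequencies and the PK analysis do not change.
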